## 5.5 Recruitment and retention strategies

This is a Phase I-II study planned for six centers. The selected centers will be responsible for subject recruitment. Recruitment will be competitive, with a proposed initial recruitment of 21 subjects per center; however, this will be contingent on the performance of each center, so this number may vary by center.

The minimum expected recruitment rate per center is 0.2 subjects per day.

Subject participation in the study is approximately 35 days, during which time they are only required to attend two visits after the baseline visit, so retention issues are not anticipated. However, subjects will be eligible for travel and travel expenses to attend their visits. Other strategies to improve subject retention include, but are not limited to:

- Clearly communicate the importance of the study and the benefits the population will gain from its results.
- Make calls or send text messages to remind yourself of appointments or activities to do.
- Provide a printed calendar and ID card to remind you of upcoming appointments and activities, as well as their estimated duration.
- Offer flexible business hours.
- Systematic organization of the study procedures, so that the subject does not stay longer than necessary during his visit.
- Minimize subject wait times.

All materials to be delivered to the subject or recruitment strategies implemented by the Centers will be submitted for approval by the corresponding committees.

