### 7.1 From the research center

This study will be conducted at research centers previously evaluated by the sponsor. These centers will be institutions or establishments that conduct health research and comply with current regulations.

The research center will be responsible for forming a multidisciplinary research team to execute the clinical study according to the protocol. It is its prerogative to design the organization and select the personnel who will perform these functions. However, the sponsor requires that the Principal Investigator (PI) be a physician specialized in ophthalmology.

Any person assigned responsibility for part of the study monitoring (coinvestigator, sub-investigator, nurse, etc.) or a specific role in the study (pharmacist, administrative assistant, study coordinator, etc.) must be listed in the "Delegation of Responsibilities."

The competency and training of all individuals directly involved in study activities must be verified prior to the conduct of any protocol-related activities. This must be recorded, and documents constituting evidence of this competency and/or training must be retained in the study master file. The competency and training of personnel involved in the study, both at the central level and at the study sites, is the responsibility of the sponsor.

The sponsor must ensure that all study center personnel participating in the study are adequately trained in the study (research protocol, investigator's manual, amendments, standard operating procedures, etc.) and in ICH Good Clinical Practices prior to the start of their participation in the study. Training must be documented in writing and filed in the study's master file.

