### 7.3 Randomization and blinding

Subject randomization will be performed using a computerized allocation system. After signing the FCI, the patient will receive a patient number, which will be used to pseudonymize all information during collection and completely anonymize it during analysis.

The generation will be carried out by a third party authorized by Laboratorios Sophia, SA de CV, through its electronic system. The information corresponding to this third party will be found in the file.

Blinding will be performed by the subject, PI, and subinvestigator. Furthermore, the statistical analysis will be performed blinded for the final analysis. Blinding cannot be guaranteed for the subject.

Masking will be done through primary and secondary packaging.

They will be identified by identical labels. These, in compliance with current and applicable regulations, must contain at least:

- Name, address and telephone number of the sponsor.
- Pharmaceutical form and route of administration.
- Batch number.
- Legend "Exclusively for clinical studies"
- Expiration date.

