#### *7.4.4.5 Corneal staining with fluorescein*

A drop of topical anesthetic is instilled into the conjunctival fornix. A second drop is then applied to the tip of the fluorescein strip, allowing it to sit on the strip for 5 seconds to elute the dye, shaking off the excess at the end. A small amount of contact is made between the strip and the conjunctiva in the temporal fornix while the patient looks upward, avoiding damaging the conjunctiva. After assessing the TRPL, 4 to 8 minutes after instillation of the dye, the corneal fluorescein staining is assessed using a slit lamp with a cobalt blue filter. It is graded according to the Sjögren's Clinical Collaboration Alliance (SICCA) Ocular Staining Grading (OSG). [42]

According to the CTO, grade 0 corresponds to the absence of punctate epithelial erosions (PEEs); grade 1 is defined as the presence of 1-5 PEEs; grade 2 corresponds to 6-30 PEEs; and >30 PEEs will be classified as grade 3. An additional grading point will be added if: 1) PEEs with a diameter of 4 mm are present in the central portion of the cornea; 2) filaments are observed; and 3) confluent staining patches, including linear staining, are observed. [42] See **Figure 4**

The IP will record in the file and with the FERC the grades awarded for corneal staining of OD and OS, respectively. The maximum grade per eye is 6.

Management as AE: Corneal staining that is greater than that recorded as baseline will be considered AE due to lack of efficacy.

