### 10.1.2 Data interpretation

The Kolmogorov-Smirnov and Shapiro-Wilk tests will be performed, as applicable, to determine whether the distribution is normal in the results obtained in each study group.

The results of continuous quantitative variables will be presented in measures of central tendency: mean, standard deviation and ranges.

The statistical analysis of continuous quantitative variables to find significant differences (  $p<0.05$  ) will be as follows:

- Intra-group analysis: will be determined using the Wilcoxon rank test for quantitative variables.
- Between-group analysis: Differences between groups will be analyzed using the Student t-test or the Mann-Whitney U statistic if applicable ( it will be used to test whether a group of data comes from the same population).

The level of difference considered significant will be an alpha ( $\alpha$ ) of 0.05 or less. A 95% CI will be considered for noninferiority criteria.

The results of the nominal and ordinal qualitative variables will be presented in frequencies, proportions and percentages.

Statistical analysis to identify significant differences in qualitative variables will be performed by creating 2x2 contingency tables and will be carried out as follows:

- Intra-group difference: McNemar's test. This test is applied to 2x2 contingency tables with a dichotomous trait, with matched pairs of subjects, to determine whether the marginal frequencies of the row and column are equal (marginal homogeneity).

- Difference between groups: Pearson's Chi-square test (  $X^2$  ) or Fisher's exact test for expected values less than 5.

The level of difference to consider significance will be an alpha ( $\alpha$ ) of 0.05 or less.

For adverse event reporting, all eyes of participants randomized to an intervention group after the baseline visit will be considered. Results will be expressed as the number of subjects.

The final results report will be displayed in tables or graphs, as appropriate.

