## 10.2 Sample size calculation

### 10.2.1 Number of subjects calculated

n= 126 evaluable subjects (both eyes)

63 subjects per arm.

An estimated 63 subjects (both eyes) are enrolled per treatment arm. During the safety phase, 24 subjects (12 from each group) will be recruited, and 102 will be recruited during the final phase, completing the sample of 126 required for the efficacy analysis.

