7.0 Methods of Analysis

Statistical analysis will be performed by staff of Laboratorios Sophia, SA de CV. The statistical program SPSS version 19.0 (IBM Corporation, Armonk, NY, USA) will be used.

The designated personnel will be blinded to the intervention groups. Coding will be performed using consecutive numbers for each intervention group.

The data will be collected and organized in an Excel spreadsheet (Microsoft® Office). The data will then be exported to the SPSS software platform. The variables will be categorized according to their nature (see Table 2).

Study participants will be identified by a number and their initials.

The initials of the subject of study will be obtained starting with the first letter of the name, followed by the first letter of the first surname and the first letter of the second surname, obtaining a maximum of three letters. In case the person has two names or a compound surname, the first letter will always be used.

Example:

to.	[name]	B. [name]
to.	Initials: AMC	b. Initials: JDO

Once the subject has been selected, they will be assigned a number that will identify them throughout the study. This code will consist of eight numbers in the following order from left to right:

- Three digits of the molecule under study according to the sponsor's designation.
- Two digits corresponding to the research center number.
- Three digits of the consecutive number assigned to its inclusion at the research center.

Subjects will be divided into two equal groups, which will be randomly and blindly assigned to one of the PI, PRO-176 or Systane® Balance (assignment 1:1). Which will be administered based on the dosage described in the protocol.

A preliminary safety analysis will be performed upon completion of follow-up of subject 12 in the Nanodrop® group (Phase I).

If fewer than 20% of unexpected drug-related AEs occur in the Nanodrop® group, enrollment for the efficacy analysis (Phase II) will be completed. Otherwise, the study will be terminated.

The results of the continuous quantitative variables will be presented in measures of central tendency: mean, standard deviation and ranges, see table 2.

The Kolmogorov-Smirnov and Shapiro Wilk test will be performed to determine whether the distribution is normal in the results obtained in each study group (Haffajee et al., 1983).

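### No named between-group test accounts for centre, although six centres recruit competitively and read the ocular signs locally

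*Protocol*

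**What the plan says.** **Centres and readers.** Protocol 5.5: "This is a Phase I-II study planned for six centers". It continues: "Recruitment will be competitive, with a proposed initial recruitment of 21 subjects per center", and adds that the number may differ with each centre's performance. Protocol 7.1: "The research center will be responsible for forming a multidisciplinary research team". On staining, Protocol 7.4.4.5 says: "The IP will record in the file and with the FERC the grades awarded for corneal staining" (IP is the protocol's abbreviation for principal investigator). Section 7.4.4.6 does the same for the conjunctiva. Section 7.4.4.4 has break-up time observed after fluorescein and entered in the clinical record and case report form. Neither document describes central reading.

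**Allocation.** Protocol 7.3: "Subject randomization will be performed using a computerized allocation system", with the list generated by an authorised third party. No list type, block scheme or stratum is given. SAP 7.0: "Subjects will be divided into two equal groups, which will be randomly and blindly assigned to one of the PI", with a 1:1 ratio.

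**Analysis.** Protocol 10.1.2: "Differences between groups will be analyzed using the Student t-test or the Mann-Whitney U statistic if applicable". Categorical outcomes get chi-square or Fisher tests. The protocol's table of operational definitions (7.4.4) assigns Mann-Whitney to the OSDI and break-up time, and chi-square or Fisher to both stains. SAP 7.0 repeats the 10.1.2 tests. SAP Table 3 carries a code for multivariate analysis against the secondary outcomes, without a model or covariates.

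**The concern.** When several centres each use their own readers, part of the spread in a graded sign can come from who read it and which patients that centre sees. A test that ignores centre leaves that part in the error term. Here such differences are plausible, though not shown. Break-up time and staining depend on judgement at the slit lamp. The documents also describe the staining scale in two ways: SICCA in Protocol 7.4.4.5, 7.4.4.6 and Annex 15.2, Oxford in the 7.4.4 table and the SAP.

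What is at stake depends on how the list is built, which the plan does not say:

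- If allocation ignores centre, the planned tests are valid but give up some precision.
- If allocation is stratified by centre, the analysis does not match the design. The unadjusted standard error then overstates the true uncertainty, and the test is stricter than its stated level.

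**Working it through.** **Inputs from the documents.** Six centres, 126 subjects, 63 per arm; OSDI standard deviation 17.1; margin 5 points; significance level 0.05, used one-sided in the sample-size formula (Protocol 5.5, 10.2.1, 10.2.2).

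**Assumed input.** The share of outcome variance due to centre, called s. The documents give no value and there is no plan figure on this point to reproduce, so a range is shown.

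**Step 1: approximate gain.** Removing the centre component multiplies the standard error by √(1 − s). The equivalent gain in subjects is 1/(1 − s) − 1.

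| s | √(1 − s) | Cut in SE | Equivalent extra subjects |
|---|---|---|---|
| 5% | √0.95 = 0.975 | 2.5% | 5.3% |
| 10% | √0.90 = 0.949 | 5.1% | 11.1% |
| 20% | √0.80 = 0.894 | 10.6% | 25% |

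**Step 2: baseline on the OSDI scale.** SE = 17.1 × √(2/63) = 3.047. With a true difference of 0, power is Φ(5/3.047 − 1.645) = Φ(−0.004), or 49.8%. That this is well under the stated 80% is a separate matter; here it only serves as the reference.

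**Step 3: simulation.** 126 subjects in six centres, either 21 each or 46/30/20/14/10/6; normal outcomes, total SD 17.1; 6,000 runs per setting. The t-test is compared with a linear model containing arm and centre, under simple allocation and under centre-stratified blocks of four. Each cell gives equal / unequal centre sizes. SE is the average reported standard error; power is for true difference 0 at one-sided 0.05.

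| s | SE: t-test, simple | SE: centre model, simple | SE: centre model, stratified | Power: t-test, simple | Power: centre model, stratified |
|---|---|---|---|---|---|
| 5% | 3.037 / 3.031 | 3.036 / 3.035 | 2.960 / 2.969 | 50.5 / 49.5% | 50.8 / 50.0% |
| 10% | 3.031 / 3.016 | 2.961 / 2.956 | 2.887 / 2.889 | 50.1 / 50.2% | 52.9 / 53.5% |
| 20% | 2.999 / 2.977 | 2.788 / 2.786 | 2.724 / 2.724 | 51.5 / 52.6% | 56.4 / 56.8% |

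Going from the t-test under simple allocation to the centre model under stratified blocks, the reported SE falls by 2.0-2.5%, 4.2-4.8% and 8.5-9.2% (for example 1 − 2.724/2.999 = 9.2%). Step 1 is therefore a slight upper bound. Changing the analysis alone, with simple allocation kept, gains nothing at 5%, 2.0-2.3% at 10% and 6.4-7.0% at 20%. Power rises by less than 1 point at 5%, about 3 points at 10% and 4-5 points at 20%. The simulation standard error of one power figure is √(0.5 × 0.5/6000), about 0.65 points.

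**Step 4: type I error, nominal 5%.**

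| s | t-test, simple | t-test, stratified | Centre model, stratified |
|---|---|---|---|
| 5% | 5.1 / 5.3% | 4.7 / 4.6% | 4.9 / 4.8% |
| 10% | 5.1 / 4.7% | 3.8 / 4.3% | 4.5 / 5.0% |
| 20% | 5.1 / 5.2% | 3.5 / 3.6% | 5.0 / 4.9% |

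The simulation standard error is about 0.28 points. A direct check at 20%, equal centres, stratified: the t-test reports an average SE of 2.991, but the estimate actually varies with SD 2.736. The effective critical value is 1.657 × 2.991/2.736 = 1.811, whose upper tail is 3.5%.

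**Limits.** The simulation uses the OSDI's SD and margin. The proportional changes in SE carry over to another roughly normal outcome with the same s. The rank tests proposed for staining were not simulated.

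**The case against.** A sponsor could fairly reply that an unadjusted comparison in a 1:1 randomised trial is valid, that the centre share is assumed, and that the primary endpoint is a patient questionnaire. Protocol 7.1 also requires site training, and 7.4.4.5 and 7.4.4.6 give counting rules that should limit differences between readers. The multivariate code in SAP Table 3 might be meant to cover centre. Most of this stands. Type I error under simple allocation is sound, the gain is negligible at a centre share of about 5%, and the argument from local readers reaches the OSDI only indirectly, if at all. But a code without model or covariates commits the analyst to nothing, and validity under simple allocation does not settle the case of a stratified list.

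Three stronger readings are tempting, and the documents do not support them.

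- *The equal splits are left to chance.* Protocol 10.2.1 says "24 subjects (12 from each group) will be recruited" in the safety phase and plans 63 per arm overall. No passage says that the list is unrestricted, and the SAP states equal groups at 1:1. The mechanism is unreported, which is a different matter. A modest imbalance would also cost little: 56/70 keeps 4 × 56 × 70/126² = 98.8% of the efficiency, and 52/74 keeps 97.0%.
- *The safety gate is affected.* The rule in Protocol 4.1 and 10.1.5 is triggered by the 12th Nanodrop subject and uses events in that arm only. The comparator count does not enter it.
- *Chance imbalance across centres biases the contrast.* Under randomisation it is random error, already reflected in the unadjusted standard error.

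**Conclusion.** The point holds as a gap in efficiency and in matching analysis to design; it is not a flaw in validity. Its size rests on an assumed centre share of variance. With stratified blocks and a centre term, the cut in standard error runs from about 2.5% at a 5% share to about 10.6% at 20% by formula, and from 2.0% to 9.2% in simulation. If the third party's list already stratifies by centre, the planned t-test runs below its nominal level once the centre share reaches about 10%. The case is strongest for break-up time and staining. For the OSDI it rests on possible differences in patients between centres and on consistency with a stratified design. The change is worth making because it is cheap and no new data are needed: Protocol 5.7 and SAP 7.0 already put the centre number in every subject code.

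**What to change.** **Protocol 10.1.2, the 7.4.4 table and SAP 7.0:** replace the unstratified between-group tests with a linear model containing arm and centre for the OSDI and break-up time, and with centre-stratified rank tests (van Elteren) for the ordinal staining grades. In SAP Table 3, either name the model and covariates behind the multivariate code or remove it.

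**Protocol 7.3:** specify randomisation in blocks of varying size, stratified by centre, so that design and analysis match. This should be settled before the first allocation. If a list already exists, state its type, blocks and strata.

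**Cost.** Six centres use 5 degrees of freedom (124 to 119 with 126 subjects; 100 to 95 with 102). If centre has no effect at all and allocation is simple, the simulated SE widens by about 2% (3.048 to 3.110 with equal centres); under stratified blocks there is practically no penalty (3.038 to 3.041). The analysis takes slightly more work: the SAP should say how very small centres are handled, and the sponsor should confirm that the named software can run the stratified rank test.

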### 7.4.2 Secondary outcome variables

- Changes in BCVA (TE: day 8 and 29)
- Changes in TRPL with fluorescein (TE: day 8 and 29)
- Corneal fluorescein staining changes (TE: day 8 and 29)
- Conjunctival staining changes with lissamine green (TE: day 8 and 29)
- Incidence of expected AEs (TE day 8 and 29)

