## 7.4.4 Definition of variables, methods and scales to be used for measurement

Variable	Guy	Unit (symbol)	Measurement method	Normal value	Evaluation time	Statistical test
Primary outcome						
OSDI	Discreet	Points (-)	Questionnaire	< 13	VB and VF	Mann-Whitney U
Unexpected EAs related to PI	Discreet	Number of cases (n)	Counting	0	VB, V1 and VF	Mann-Whitney U
Unexpected AEs related to the PI (bis)	Nominal categorical	Present/absent (-)	Observation	Absent	VB, V1 and VF	$\chi^2$ or Fisher's exact test
Of secondary outcome						
MAVC	Discreet	Fraction (-)	Snellen chart	1	VB, V1 and VF	Mann-Whitney U
TRPL with fluorescein	Continue	Seconds (s)	Direct observation with slit lamp and blue filter	>10s	VB, V1 and VF	Mann-Whitney U
Corneal staining with fluorescein	Ordinal	Degrees (-)	Direct observation with a slit lamp on the Oxford scale	0	VB, V1 and VF	$\chi^2$ or Fisher's exact test
Conjunctival staining with lissamine green	Ordinal	Degrees (-)	Direct observation with slit lamp and cobalt blue filter, Oxford scale graduation	0	VB, V1 and VF	$\chi^2$ or Fisher's exact test
EA	Discreet	Number of cases (n)	Counting	0	VB, V1 and VF	Mann-Whitney U
EA (repeat)	Nominal categorical	Present/absent (-)	Observation	Absent	VB, V1 and VF	$\chi^2$ or Fisher's exact
Exploratory						
Number of applications made daily	Discreet	Number of applications (n)	Count by Subject's Diary	>4	V1 and VF	Mann-Whitney U

**Table 2**Operational definition of variables

The variables, method, and scales for their measurement are described in detail below. They are listed in order according to **Table 2**

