The statistical analysis of continuous **quantitative variables** to find significant differences (p) will be as follows:

- Intra-group analysis: will be determined using the Wilcoxon rank test, for quantitative variables (Woolson, 2008).
- Between-group analysis: differences between groups will be analyzed using the Student t-test or the Mann-Whitney U statistic if applicable (it will be used to test whether a group of data comes from the same population).

The level of difference to consider significance will be an alpha (α) of 0.05 or less. It will be considered a 95% CI for non-inferiority criteria (Schumi & Wittes, 2011; Easty et al., 2006).

The result of the nominal and ordinal qualitative variables will be presented in frequencies, proportions and percentages, see table 2.

Statistical analysis to identify significant differences in **qualitative variables** will be performed by creating 2x2 contingency tables and will be carried out as follows:

- Intra-group difference: McNemar's test (Klingenberg & Agresti, 2006). This test is applied to 2x2 contingency tables with a dichotomous trait, with matched subject pairs, to determine whether the marginal frequencies of the row and column are equal (marginal homogeneity).
- Difference between groups: Chi-square test (χ^2) Pearson's or Fisher's exact test in values expected under 5.

The level of difference to consider significance will be an alpha (α) of 0.05 or less.

For the reporting of adverse events, all eyes of participants who were randomized to an intervention group after the baseline visit will be considered.

The final results report will be displayed in tables or graphs, as appropriate.

Subjects who meet a minimum adherence of 70% will be included in the statistical analysis to meet the study objective, based on the weight of the PI. In cases where the container is not returned or has not been physically intact, adherence will be measured using the subject's diary.

The investigational drug will be considered safe and effective when there are no clinical and statistical differences in all primary outcome variables, with respect to its comparator.
(Systaine® Balance).

Table 3. Triangulation of concepts

Variable Type	Variable	A1	B1	B2	C1	C2	D1	E1	E2	E3
Background										
A1	Demographics						DT			
Basal										
B1	Medical record				DT					
B2	Comprehensive ophthalmological evaluation				DT		TB	TB		TB
Security										
C1	Unexpected/related AEs				TB		TB		TB	TB
C2	EAs				TB		TB		TB	TB

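### Ordinal staining grades are to be tested in 2x2 tables with no stated cut-point, which costs power and leaves the cut open to choice

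*Protocol*

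**What the plan says.** Protocol 10.1.2 treats nominal and ordinal variables as one class: "The results of the nominal and ordinal qualitative variables will be presented in frequencies, proportions and percentages". It then states that testing of qualitative variables "will be performed by creating 2x2 contingency tables". Between arms the test is Pearson chi-square, or "Fisher's exact test for expected values less than 5". Within arms it is McNemar, of which the protocol says "This test is applied to 2x2 contingency tables with a dichotomous trait". SAP 7.0 gives the same rule, with tests "performed by creating 2x2 contingency tables".

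The operational-definition table in Protocol 7.4.4 classes both staining variables as ordinal and assigns chi-square or Fisher. Protocol 7.4.2 lists both as secondary outcomes, expressed as changes at days 8 and 29.

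The documents do not agree on the scale. Protocol 7.4.4.5 and 7.4.4.6 grade each eye on the SICCA scale; for the cornea, "The maximum grade per eye is 6", and the conjunctival maximum is the same. That gives seven levels, 0 to 6. The table in 7.4.4 instead specifies, for the cornea, "Direct observation with a slit lamp on the Oxford scale", and names Oxford for the conjunctiva too. SAP 6.0 and Annex 10.2 also use Oxford, with 0–5 per panel and 0–15 in total.

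**The concern.** A 2x2 table needs two outcome classes, and a scale with six, seven or sixteen levels does not supply them. Someone has to choose where to cut, and whether to cut the visit grade or the change from baseline. The plan settles neither.

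Two things are at stake. Collapsing the grades discards their order on either side of the cut, so the comparison has less power than a test that keeps all levels. And two analysts following the plan faithfully could cut in different places and report different p-values. If the cut were picked after the results had been seen, the nominal 5% level would no longer hold. Two of the four secondary efficacy variables are involved.

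**Working it through.** **1. Is a cut-point stated anywhere?** Thresholds for staining appear in five places, each for another purpose:

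- a normal value of 0 (table in Protocol 7.4.4);
- more than 5 corneal sites for eligibility, i.e. SICCA grade 2 or higher (Protocol 5.1.1 with 7.4.4.5);
- more than 9 conjunctival sites for eligibility, i.e. SICCA grade 1 or higher in a zone (5.1.1 with 7.4.4.6);
- any corneal rise above baseline, reported as an adverse event (7.4.4.5);
- a conjunctival score of 3 or more that is above baseline, reported as an adverse event (7.4.4.6).

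None is named as the cut for the efficacy analysis.

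**2. Is there a planned figure to reproduce?** No. The sample size rests on OSDI only, and the documents give no staining distribution, effect or power. The numbers below therefore rest on assumed distributions. From the documents come the numbers per arm (63 planned, Protocol 10.2.1; 51 evaluable, Protocol 10.1.4), the 0.05 level (taken as two-sided) and the chi-square/Fisher rule.

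**3. Information kept by one cut.** For a small proportional-odds shift, the efficiency of one cut relative to the rank test is 3c(1−c) / (1 − Σp³), where c is the share of subjects below the cut and p are the level proportions.

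- Uniform, 7 levels: Σp³ = 7 × (1/7)³ = 0.020. Central cut, c = 0.429: 3 × 0.429 × 0.571 / 0.980 = 75% kept. End cut, c = 0.143: 37.5%.
- Bell-shaped: 71.5% at c = 0.35, 15% at c = 0.05.
- Low-skewed: 72% at c = 0.35, 3% at c = 0.99.
- Floor-heavy: 83.5% at c = 0.45, 3% at c = 0.99.
- Uniform, 6 levels (one Oxford panel): 77% at c = 0.5, 43% at c = 0.167.
- Normal latent scale: efficiency is φ(z)²/[q(1−q)] divided by 3/π. At the median, 0.637/0.955 = 67%; at a 10/90 cut, 0.342/0.955 = 36%.

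A central cut therefore keeps about 67–83%, a loss of about 17–33%. The loss passes one half once less than about a fifth of subjects lie on one side.

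**4. Power.** I assumed seven levels with cumulative proportions 0.15, 0.40, 0.65, 0.82, 0.92 and 0.98, a shift of 0.53 SD on a latent normal scale, and one value per subject. Each row is 20,000 simulated trials, with Fisher used when an expected count is below 5.

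| Per arm | Shift | Mann-Whitney | Cut 1 | Cut 2 | Cut 3 | Cut 4 | Cut 5 | Cut 6 |
|---|---|---|---|---|---|---|---|---|
| 63 | up | 81% | 38% | 61% | 68% | 59% | 45% | 9% |
| 63 | down | 80% | 55% | 68% | 59% | 43% | 15% | <1% |
| 51 | up | 72% | 29% | 52% | 59% | 50% | 36% | 5% |
| 51 | down | 71% | 47% | 60% | 50% | 35% | 8% | <1% |

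The shift was sized to give the rank test about 80% power at 63 per arm. That 80% is a benchmark, not a property of this trial.

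A second set of simulations (8,000 trials each) used the shapes in step 3 with a common odds ratio of 2.5. At 63 per arm the rank test had 81–82%, the best single cut 72–74% and the worst cut between under 1% and 35%. At 51 per arm the rank test had 72–75%.

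**5. Type I error if the most favourable cut is reported.** With no true difference, the chance that at least one cut gives p < 0.05 was 17–18% for the step 4 distribution. For the step 3 shapes it was 20% (uniform), 17–18% (bell), 15–18% (low-skewed), 14–15% (floor-heavy) and 17–18% (uniform, 6 levels). The rank test stayed at about 5% throughout.

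**The case against.** Several stronger readings are tempting, and the documents do not support them.

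- *Most of the information is thrown away.* Only for a badly placed cut. A central cut keeps two thirds or more, and in step 4 the best cut costs about 12–13 percentage points of power at 63 per arm.
- *The baseline is ignored.* McNemar is a paired test, and the outcomes are defined as changes, so a dichotomised change would use the baseline. The gap is narrower: the plan does not say which quantity is cut.
- *The false-positive rate is inflated.* It is inflated only if the cut is chosen on the results. Protocol 10.1.1 and SAP 7.0 keep the analyst blinded to coded groups. That limits choosing a cut because it favours one product, but it does not prevent choosing one because it is significant.
- *The trial's conclusion is at risk.* It is not. Staining is secondary, and SAP 7.0 ties its safe-and-effective decision to the primary outcome variables.
- *The scale has seven levels.* That is true of the SICCA text only. The Oxford entries give other counts, though the six-level check leads to the same conclusion.

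It is also fair to say that the table in Protocol 7.4.4 asks only for chi-square or Fisher, which would allow a table with all grades. The 2x2 restriction comes from Protocol 10.1.2 and SAP 7.0, and a chi-square on the full table would still ignore the order of the grades. SAP Table 3 lists descriptive, bivariate and multivariate codes for staining beside the 2x2 code, but names no model. These points limit the concern without supplying a cut-point.

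**Conclusion.** The point holds in a limited form. Both documents send ordinal staining grades to 2x2 tests, with no cut-point and no statement of whether grade or change is dichotomised. The cost is a loss of about 17–33% of the information at a central cut and more than half at a cut near a tail. In the assumed example, power goes from about 80% to about 40–70% at 63 per arm, and from just over 70% to about 30–60% at 51, with the outermost cuts worse still. Selecting the cut on the results could raise the type I error to about 14–20%.

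The absence of a cut-point is a matter of text and needs no assumption. The sizes rest on assumed distributions and shifts and on one value per subject; correlation between a subject's two eyes was not modelled. The direction was the same for every shape tried. The effect is confined to two secondary efficacy variables.

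**What to change.** 1. Reconcile the scale: name SICCA or Oxford once, and use it in Protocol 7.4.4 (table and text), SAP 6.0 and the annexes.
2. Define one value per subject, since grades are recorded per eye: for example the mean of the two eyes, or the worse eye, fixed in advance.
3. Between arms, use Mann-Whitney on change in grade, or a proportional-odds model for the visit grade with baseline grade as covariate. Name one as the main analysis.
4. Within arms, use Wilcoxon signed-rank in place of McNemar.
5. Keep 2x2 tests for truly binary variables such as adverse event present or absent.

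If a responder-type summary is still wanted, state one cut and its reason before unblinding, and say whether it applies to the grade or to the change.

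The plan already assigns Mann-Whitney to OSDI, visual acuity and break-up time, and Wilcoxon to within-group comparisons of quantitative variables. The change is therefore wording in Protocol 7.4.4 and 10.1.2 and in SAP 6.0 and 7.0, with no new data or software. The small real cost is agreeing the scale and the two-eye rule first.
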